9.4.5. Electrocardiograms

- Triplicate 12-lead ECGs will be obtained in the study at the time points detailed in the SoA and at other times in the study if clinically indicated (Section 2.3; single ECGs at all other time points) using an ECG machine that automatically calculates the heart rate and measures PR, QRS, QT, and QTcF intervals. Refer to Section 8.1.2 for QTc withdrawal criteria and additional QTc readings that may be necessary.
- At each time point at which triplicate ECG are required, 3 individual ECG tracings should be obtained as closely as possible in succession, but no more than 4 minutes apart. The full set of triplicates should be completed in less than 8 minutes.
- Holter monitoring will be performed at screening only. This 24-hour Holter will be performed to eliminate participants with non-clinically overt cardiac arrhythmias or other exclusionary criteria.

9.4.6. Cardiac Telemetry

Continuous cardiac telemetry will be performed in the study at the time points detailed in the SoA and at other times in the study if clinically indicated as detailed in the SoA (Section 2.3).

9.4.7. Clinical Safety Laboratory Assessments

- Refer to Appendix 2 for the list of clinical laboratory tests to be performed and to the SoA for the timing and frequency.
- The investigator must review the laboratory report, document this review, and record any clinically relevant changes occurring during the study in the AE section of the CRF. The laboratory reports must be filed with the source documents.
- All laboratory tests with values considered clinically significantly abnormal during participation in the study or within 7-14 days after the last dose of study treatment should be repeated until the values return to normal or baseline or are no longer considered significantly abnormal by the investigator or medical monitor.
- If such values do not return to normal/baseline within a period of time judged reasonable by the investigator, the etiology should be identified and the sponsor notified.
- All protocol-required laboratory assessments, as defined in Appendix 2, must be conducted in accordance with the laboratory manual and the SoA.
- If a cardiac arrhythmia occurs, a PK sample and drugs of abuse test should be taken as close to the time of the event as possible.
- Laboratory results at Day -1 are for the purposes of providing baseline values prior to dosing. The review of laboratory abnormalities at Day -1 for eligibility will be based on Investigator discretion and clinical judgement.

9.4.8. Participant Diary Card

Participants will be given a diary card for them to record the healing time of the blisters as well as to record any adverse events or medications taken whilst outside of the unit.

9.5. Pharmacokinetics

9.5.1. Blood sample collection and analysis

- Blood will be collected into appropriate tubes (type to be confirmed pending ongoing stability investigations) for measurement of GSK3358699 and GSK3206944 concentrations in plasma (approximately 1 mL per time-point up to and including 6 hours post dose and approximately 2 mL per time-point after 6 hours post-dose). **[S1]** and **[S2]**
- Blood (6 mL per time point) will be collected into sodium heparin tubes for the isolation of monocytes and for measurement of GSK3206944 concentrations in monocytes, as specified in the SoA. **[S3]**

- Instructions for the processing, storage and shipping of biological samples will be provided by the sponsor in the SRM. The actual date and time (24-hour clock time) of each sample will be recorded.
- Samples will be used to evaluate the PK of GSK3358699 and GSK3206944 in plasma and GSK3206944 in monocytes. Samples collected for analyses of GSK3358699 and GSK3206944 plasma concentration may also be used to evaluate safety or PD aspects related to concerns arising during or after the study.
- Once the plasma has been analyzed for GSK3358699 and GSK3206944 any remaining plasma will be analyzed qualitatively for other compound-related metabolites and the results reported under a separate protocol. **[E4]**
- Genetic analyses will not be performed on these plasma samples unless consent for this was included in the informed consent. Participant confidentiality will be maintained.

Drug concentration information that may unblind the study will not be reported to the investigator site or blinded personnel until the study has been unblinded.

9.5.2. Urine Sample Collection and Analysis

• Urine will be collected for qualitative analysis of compound-related metabolites according to the SoA time points. Immediately prior to dosing, each participant will be instructed to void their bladder into a collection container and no more than 20 mL of this urine sample will be retained as a pre-dose control sample. A 0-24 hour urine collection will begin immediately following dose administration. Participants will be instructed to collect all urine voided on each occasion into a collection container and the urine will be transferred / pooled in a 0-24 h storage container for further processing after the end of the collection period, with the exception of the samples required for urinalysis testing during this period which will be collected separately. Further instructions on urine sample processing, storage and shipment will be provided in the SRM. The results of this analysis will be reported under a separate protocol. **[E4]**.

9.6. Pharmacodynamics

There will be several measures of PD taken in the study using whole blood or bloodderived samples, as outlined in the SoA.

9.6.1. Ex vivo PD sample

1 mL whole blood samples will be collected according to the timings specified in the SoA. At each timepoint, one 1mL sample will be drawn into a TruCulture tube containing LPS and a second 1mL sample will be drawn into a 1 "GSK3358699 LPS" TruCulture tube, and incubated for 24 hours. For all samples, cellular and soluble contents will be separated and inflammatory mediators (MCP-1, IL-6 and TNF) analysed in the soluble fraction. **[S4]**

9.6.2. Circulating inflammatory biomarkers / proteins

Approximately 2 mL of blood will be collected into heparin tubes according to the timings on the SoA. This will allow for analysis of plasma to measure inflammatory mediators, such as MCP-1, IL-12p40 and MMP-9. Measurement of soluble inflammatory mediators will be carried out in batch analysis. **[E1a]**

9.6.3. Gene array panel

Approximately 2.5 mL of blood will be collected into PAXgene tubes for gene array analysis according to the timings on the SoA. Samples will be used to extract ribonucleic acid (RNA) and prepare complementary deoxyribonucleic acid (cDNA) which will subsequently be used for analysis by gene array panels. **[E1b]**

Other measures of pharmacodynamics will be measured as part of the in vivo challenges (LPS, GM-CSF or cantharidin) and the measurements are described in Biomarkers in Section 9.8.

9.7. Genetics

All randomized subjects will be required to provide a 2 mL blood sample for potential companion diagnostic development, if test development is required by regulatory authorities to identify subjects who are appropriate for GSK3358699 treatment. This 2 mL blood sample will be stored frozen at the central lab.

All randomized subjects will be required to provide a 6 mL blood sample for investigation of genetic variation of genes that encode carboxyesterase (CES) according to the timings on the SoA **[E5]**. Additionally, this sample will be used for additional genetics research for those participants who have consented in the optional exploratory genetics analysis component of the study.

In the event of DNA extraction failure, a replacement genetic blood sample may be requested from the participant. Signed informed consent will be required to obtain a replacement sample unless it was included in the original consent.

See Section 12.6 Appendix 6 for information regarding genetic research. Details on processes for collection and shipment and destruction of these samples can be found in the SRM.

9.8. Biomarkers

There will be several different types of biomarker samples collected during the study as outlined in the SoA, including biomarkers from blood and blister fluid. The biomarkers will be induced using the inflammatory stimuli (LPS, GM-CSF, cantharidin) as described in Section 5.1. The biomarkers will include cellular and soluble proteins and gene expression, and the effect of GSK3358699 on these measures of inflammation will be determined.

9.8.1. Biomarkers in blood

Biomarkers in blood will be collected pre- and post- challenge (*in vivo* challenge with LPS or GM-CSF). Cellular and soluble activation markers will be determined at several time points as specified in the SoA. Leukocyte counts for each sample will be recorded in the eCRF. **[E2]**

9.8.1.1. Cellular activation markers blood sample (all cohorts in Part C)

Approximately 2 mL of blood will be collected into heparin tubes for measurement of leukocyte number and activation markers by flow cytometry (see indicative list in endpoints) **[E2b]**.

9.8.1.2. Circulating inflammatory biomarkers blood sample (challenge cohorts only)

Approximately 2 mL of blood will be collected into heparin tubes according to the timings on the SoA. This will allow for analysis of plasma to measure inflammatory mediators. Methods of analysis which may be used on these samples are detailed in the SRM. Measurement of soluble inflammatory mediators will be carried out in batch analysis. **[E2a]**

9.8.1.3. Gene array panels (challenge cohorts only)

Approximately 2.5 mL of blood will be collected into PAXgene tubes for gene array analysis according to the timings on the SoA. Samples will be used to extract RNA and prepare cDNA which will subsequently be used for analysis by gene array panels to determine the effects of compound on challenge with LPS or GM-CSF. **[E2d]**

9.8.2. Biomarkers in blisters

Biomarkers in blisters will be collected by piercing the blister with a needle and aspirating the blister contents with a pipette into a polypropylene micro-centrifuge tube. Cellular and soluble contents will be separated. The volume of the blister sample will be calculated and recorded in the eCRF. **[E3]**. The baseline blister samples collected will be repeated if > 4 months elapses between the baseline blister and the challenge treatment Period (eg if a reserve in the study is not dosed and is subsequently rescreened for a later cohort).

9.8.2.1. Cellular blister sample

Blister sample will be used to measure leukocyte number and activation markers by flow cytometry (see indicative list in Section 4), at times specified in the SoA **[E3]**.

9.8.2.2. Soluble blister sample

The soluble fraction from the blister sample will be used to measure inflammatory mediators. Methods of analysis which may be used on these samples are detailed in the SRM **[E3]**.

9.8.3. RNA Expression Research of a Subset of RNA Species

As detailed in Section 9.6.3 and Section 9.8.1.3, samples will be used to extract RNA and prepare cDNA which will subsequently be used for analysis by gene array panels. **[E1b, E2d]**

9.9. Health Economics OR Medical Resource Utilization and Health Economics

This is not applicable to this study.

10. STATISTICAL CONSIDERATIONS

10.1. Hypotheses

As the primary objective of the study is to assess the safety of GSK3358699 in healthy volunteers, there are no formal hypotheses. There are also no formal hypotheses to be tested for the single or repeat dose PK data.

An estimation approach will be used to quantify the single dose PK for each dose level studied, the food effect and also to assess PK parameters following 14 days repeat dosing relative to single dosing.

10.2. Sample Size Determination

10.2.1. Sample size assumptions

At each dose level studied in Part A there will be approximately nine participants; six randomised to each of the GSK3358699 treatment groups and three receiving placebo in any one period. In Part A, each participant will be randomised to one of three sequences for the dose escalation phase.

In Part B of the study there will be approximately six participants, all receiving GSK3358699 (randomised to either fed or fasted administration), each participant will be randomised to one of two sequences. In Part C approximately fourteen participants in Cohort 4 were planned (ten randomised to the GSK3358699 treatment group and four receiving placebo, in a 5:2 ratio). In Cohorts 5 - 7 approximately eighteen participants are planned (nine randomised to each of the GSK3358699 treatment groups and nine receiving placebo, in a 1:1 ratio) and in Cohort 8 approximately twenty subjects are planned (ten randomised to the GSK3358699 treatment group and ten receiving placebo, in a 1:1 ratio).

Refer to Section 7.2 for further information on sample size and randomisation changes in the event of any dose modifications.

The sample size is based on feasibility.

The primary objective of the study is safety, where the number of safety events would be of interest, for example the number of participants experiencing a particular adverse event. At each dose level in Part A six participants will receive GSK3358699. If 0/6 of a

particular safety event in the GSK3358699 group is observed, using a Bayesian approach to determine the credible interval around an observed safety event, we would assume a flat Beta (1,1) prior, and if we were to observe 1 safety event in 6 then the posterior distribution would be Beta (2, 6), where we can be 95% certain that the true probability of the safety event lies between 0.04 and 0.58.

Sample size sensitivity

A sample size sensitivity analysis has been conducted on the primary endpoint, to investigate different safety event rates. If the number of subjects who completed each active dose reduces, then the true incidence rates of safety events that could not be ruled out would change. These changes are outlined below:

N on GSK3358699 Completing Cohort	Number of a particular safety event observed with GSK3358699	Upper limit of exact 95%CI indicating that a true incidence rate of x% could not be ruled out
6	2	71%
6	3	82%
	0	46%
5	1	64%
	2	78%
	0	52%
4	1	72%
	2	85%

Sample size re-estimation

There is no sample size re-estimation planned.

10.3. Populations for Analyses

For purposes of analysis, the following populations are defined:

Population	Description
Enrolled	All participants who sign the ICF.
Randomized	All participants who are randomised into the study and receive a randomisation number.
Evaluable	A participant is considered evaluable if they complete both screening and all their planned treatment Periods in Part A; both Periods in Part B, or the 14 day treatment Period and subsequent assessment Period in Part C.
Safety	All randomized participants who take at least 1 dose of study treatment. Participants will be analyzed according to the treatment they actually received.
Pharmacokinetic	All participants in the Safety Population who receive an active dose and for whom a PK sample was obtained and analysed.

Population	Description
PK/PD	The Safety Population will be used so that participants receiving
	placebo can be included.

10.4. Statistical Analyses

Parts A, B and C will be reported separately in the outputs.

10.4.1. Safety Analyses

All safety analyses will be performed on the Safety Population.

Endpoint	Statistical Analysis Methods	
Primary	Will be presented in tabular and/or graphical format and summarised descriptively according to GSK's Integrated Data Standards Library standards.	

10.4.2. Pharmacokinetic Analyses

All PK analyses will be performed on the Pharmacokinetic Population.

Endpoint	Statistical Analysis Methods		
Secondary	Plasma GSK3358699 and the metabolite GSK3206944 concentration- time data will be analysed by non-compartmental methods. Calculations will be based on the actual sampling times recorded during the study. Concentration-time data will be listed for each participant and treatment and summarized by planned time point and treatment.		
	From the plasma concentration-time data, the following pharmacokinetic parameters will be determined, as data permit: maximum observed plasma concentration (C_{max}), time to C_{max} (t_{max}), area under the plasma concentration-time curve [AUC ₍₀₋₂₄₎ , AUC _(0-t) and AUC _(0-∞)], and apparent terminal phase half-life ($t_{1/2}$).		
	PK parameters will be listed for each participant and treatment and summarized descriptively by treatment using the PK population. For each of these parameters, except t_{max} , the following summary statistics will be calculated for the active treatment group at each cohort: median, maximum, minimum, arithmetic mean, 95% confidence interval (CI) for the arithmetic mean, standard deviation, coefficient of variation, geometric mean, 95% confidence interval for the geometric mean and standard deviation of logarithmically transformed data. For t_{max} , median, maximum, minimum, arithmetic mean and standard deviation will be calculated. The first point, last point and number of points used in the determination of lz will be included on the listing of the derived parameters.		

Endpoint	Statistical Analysis Methods			
	Part A: Dose proportionality will be assessed by analysis of log_{e^-} transformed parameters $AUC_{(0-\infty)}$ [or if not available $AUC_{(0-t)}$] and C_{max} using the power model. Further details will be included in the RAP.			
	Part B: A mixed effects model will be fitted on the log _e -transformed parameters $AUC_{(0-\infty)}$ [or if not available $AUC_{(0-t)}$] and C_{max} with fed status as a fixed effect and participant as a random effect. Point estimates and corresponding 90% CIs will be constructed for GSK3358699 fed - GSK3358699 fasted using the residual variance. These will then be back transformed to provide point estimates and corresponding 90% CIs for the geometric mean ratio GSK3358699 fed to GSK3358699 fasted.			
	Part C: The extent of accumulation after repeat dosing, the observed accumulation ratio (Ro) will be determined. The plasma steady state ratio (Rs) and an assessment of plasma steady state across the trough concentrations will also be made. Dose proportionality will be assessed using similar methods to the single dose Part A.			

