9. PHARMACOKINETIC ANALYSES

The PK analyses described below will be carried out for GSK3358699 and GSK3206944 (acid metabolite) if the latter is quantifiable.

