9.1.5. Statistical Analyses / Methods

Details of the planned displays are presented in Appendix 9: List of Data Displays and will be based on GSK Data Standards and statistical principles.

Unless otherwise specified, endpoints / variables defined in Section 9.1 will be summarised using descriptive statistics, graphically presented (where appropriate) and listed.

9.1.5.1. **Dose proportionality (Part A)**

Dose proportionality will be assessed for GSK3358699 by visual inspection of:

- Part A (single dose - fasted state): dose normalised AUC(0-∞) [or if not available AUC(0-t)] and Cmax values versus dose.

If data permits, dose proportionality may also be assessed for GSK3358699 using the power model described below.

Dose proportionality (Parts A and C)			
Endpoints			
• Part A (single dose - fasted state): AUC(0-t), AUC(0-∞) and Cmax			
Model specification			
• Power model (log-log linear model):			
$y = \alpha \times dose^{\beta} \iff \log_e(y) = \log_e(\alpha) + \beta \times \log_e(dose)$			
Where			
\circ y = endpoint of interest			
\circ dose = actual dose received under fasted condition			
$\circ \beta$ = parameter associated to dose (slope)			
$\circ \alpha$ = participant-specific random effect (intercept)			
• Terms fitted in the power model:			
• Response: log transformation of the endpoint of interest $\log_e(y)$			

207546

- Fixed continuous covariates: $\log_e(dose)$
- Random: participant
- The Kenward and Roger method for approximating the denominator degrees of freedom and correcting for bias in the estimated variance-covariance of the fixed effects will be used.
- An unstructured covariance structure on the random effects terms (SAS: G matrix, random statement) will be used.

Model checking & diagnostics

- Normality assumptions underlying the model used for analysis will be examined by obtaining a normal probability plot of the residuals and a plot of the residuals versus the fitted values (i.e. checking the normality assumption and constant variance assumption of the model, respectively) to gain confidence that the model assumptions are reasonable.
- If there are any departures from the distributional assumptions, alternative models will be explored using appropriate transformed data.

Model results presentation

Table of the estimated slopes and 90% CI (slope close to 1 implies dose proportionality). The following will be derived:

- Fold-increase for doubling dose: 2^{β} , where β is the slope

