13.9.7. Pharmacokinetic Tables

Part A

Phar	Pharmacokinetic: Tables							
No.	Population	IDSL / Example Shell	Title	Programming Notes	Deliverable [Priority]			
PK C	oncentration	Data	•	•				
3.1.	РК	PK01	Part A: Summary of Plasma Pharmacokinetic Concentration-time Data by Compound (GSK3358699 or GSK3206944)	By treatment group and compound (GSK3358699 or GSK3206944).	SAC			
3.2.	РК	PK01	Part A: Summary of Intracellular Pharmacokinetic Concentration-time Data	By treatment group.	SAC			
3.3.	РК	PK01	Part A: Summary of Intracellular Molar Concentration Pharmacokinetic Concentration-time Data	By treatment group.	SAC			
PK D	erived Param	eters	·	•				
3.4.	РК	PK06	Part A: Summary of Derived Plasma Pharmacokinetic Parameters (Non-transformed and Log-transformed) by Compound (GSK3358699 or GSK3206944)	By treatment group and compound (GSK3358699 or GSK3206944).	SAC			
Dose	Proportionali	ty						
3.5.	РК	[Non standard] PK_T1	Part A: Summary of Estimated Slope and 90% CI of Dose Proportionality Model	By endpoint (AUC(0-t), AUC(0- ∞), Cmax).	SAC			

Part C	·				
Phar	macokinetic: '	Fables			
No.	Population	IDSL / Example Shell	Title	Programming Notes	Deliverable [Priority]
PK C	oncentration	Data			
3.6.	РК	PK01	Part C: Summary of Plasma Pharmacokinetic Concentration-time Data by Compound (GSK3358699 or GSK3206944)	By treatment group and compound (GSK3358699 or GSK3206944).	SAC
3.7.	РК	PK01	Part C: Summary of Intracellular Pharmacokinetic Concentration-time Data	By treatment group.	SAC
3.8.	РК	PK01	Part C: Summary of Intracellular Molar Concentration Pharmacokinetic Concentration-time Data	By treatment group.	SAC
PK D	erived Param	eters			• •
3.9.	РК	PK06	Part C: Summary of Derived Plasma Pharmacokinetic Parameters (Non-transformed and Log-transformed) by Compound (GSK3358699 or GSK3206944)	By treatment group and compound (GSK3358699 or GSK3206944).	SAC

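### The SAP confines dose proportionality to the parent drug and makes the power model optional, so it specifies no slope or confidence interval for the plasma acid metabolite, and it does not declare the change

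*Protocol*

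**What the plan says.** **Protocol 10.4.2.** The section opens with both analytes: "Plasma GSK3358699 and the metabolite GSK3206944 concentration- time data will be analysed by non-compartmental methods". AUC, Cmax and the other parameters come from those data. It then says: "Part A: Dose proportionality will be assessed by analysis of" log-transformed AUC(0-∞), or AUC(0-t) if that is not available, and Cmax with the power model. The commitment carries no condition and names no analyte, and further detail is left to the analysis plan. For Part C: "Dose proportionality will be assessed using similar methods to the single dose Part A".

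**SAP 9.** "The PK analyses described below will be carried out for GSK3358699 and GSK3206944 (acid metabolite) if the latter is quantifiable".

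**SAP 9.1.5.1**, which lies below that statement. "Dose proportionality will be assessed for GSK3358699 by visual inspection of" dose-normalised AUC and Cmax against dose. Then: "If data permits, dose proportionality may also be assessed for GSK3358699 using the power model described below".

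**SAP 13.9.7.** Table 3.5, "Part A: Summary of Estimated Slope and 90% CI of Dose Proportionality Model", is listed as a deliverable. Its programming note gives a split by endpoint only. Table 3.4, the descriptive summary of derived plasma parameters, is specified "By treatment group and compound (GSK3358699 or GSK3206944"), and Table 3.1 likewise.

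**SAP 2.1.** The listed changes from the protocol are the analysis populations, the removal of exploratory analyses and the reduction of Part B to listings. Dose proportionality is not mentioned.

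**The concern.** The SAP gives two answers to one question. The general statement in SAP 9 brings the acid into every PK analysis that follows, and 9.1.5.1 then names only the parent, twice. A programmer cannot tell whether Table 3.5 should hold one compound or two, or whether the power model is required at all.

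At stake is the dose-exposure description of the plasma acid. Its PK profile is secondary objective S2, and Protocol section 3 describes it as a potent BET inhibitor formed from the parent by CES-1. Because the acid is formed by a separate step, the parent's slope does not determine the acid's. The protocol's estimation approach would give the acid its own slope and interval. Under 9.1.5.1 the acid gets descriptive statistics by dose group and nothing that pools the dose levels.

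**Working it through.** No figure in the plan is in dispute, so there is none to reproduce. The check is a comparison of text, followed by a calculation of whether an acid slope would be informative.

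**1. Which analytes does the protocol's power model cover?** The sentence does not say. Two features favour both. It refers to parameters that the preceding paragraphs derive for both analytes. The Part B sentence refers to its parameters in the same unlabelled way, and objective S5 requires the food effect on both compounds. The parent's name in the Part B fed/fasted contrast matches the treatment labels in Protocol 7.3, so it need not restrict the analyte. Nothing in 10.4.2 limits proportionality to the parent.

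**2. What changed?**

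| Item | Protocol 10.4.2 | SAP 9.1.5.1 and Appendix 9 |
|---|---|---|
| Power model | Committed | Conditional and optional |
| Analyte | Not limited | Parent only, against SAP 9 |
| Visual inspection | Not mentioned | Committed, parent only |
| Slope table | Not specified | Table 3.5, by endpoint, no compound split |
| Dose-normalised plot | Not specified | None: Figures 3.1 to 3.18 are all concentration plots |
| Declared in SAP 2.1 | n/a | No |

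The one committed assessment therefore has no figure in the display list, while the optional model has a listed table.

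**3. Could Part A estimate an acid slope?**

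*Inputs from SAP 2.3.* Cohort 1 received 1, 10 and 40 mg; Cohort 2 received 3, 20 and 30 mg. Each has nine participants, each taking two active doses in Periods 1 to 3. In Period 4, six per cohort receive 25 mg.

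Profiles: 18 × 2 = 36 from Periods 1 to 3; adding 6 × 2 = 12 gives 48.

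*Model.* log(y) = log(α) + β log(dose), with a random participant intercept, as in 9.1.5.1. The slope variance is the slope element of (Σ Xᵢ′Vᵢ⁻¹Xᵢ)⁻¹, where Vᵢ has the within-participant variance on the diagonal and the between-participant variance added to every entry.

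*Assumptions.* The documents give no variability. I took within-participant CV of 20% or 40% and between-participant CV of 30% or 60%, with variance ln(1 + CV²) and a t quantile on 17 df (1.74) as an approximation.

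| Profiles | Within CV | SE of slope | 90% half-width |
|---|---|---|---|
| 36 | 20% | 0.029 | 0.05 |
| 36 | 40% | 0.053 to 0.056 | 0.09 to 0.10 |
| 48 | 20% | 0.026 | 0.05 |
| 48 | 40% | 0.049 to 0.050 | 0.09 |

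The ranges show the effect of between-participant CV, which is small.

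*If the acid is not quantifiable at every dose.* SAP 9 leaves this open. Suppose it can be measured only from 10 mg. The 1 and 3 mg profiles drop out and the dose range shrinks from 40-fold to 4-fold. With Period 4 included and assumed log-scale between/within SDs of 0.2/0.15, 0.3/0.25 and 0.4/0.4, the half-widths are 0.11, 0.18 and 0.29. Over the full range the same SDs give SEs of 0.020, 0.033 and 0.052; multiplied by 1.645, these are half-widths of 0.033, 0.054 and 0.086.

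*On the scale the SAP reports.* For a doubling of dose the fold-increase is 2^β. Around β = 1, a half-width of 0.05 spans 2^0.95 to 2^1.05 = 1.93 to 2.07; 0.10 spans 1.87 to 2.14; 0.29 spans 1.64 to 2.45.

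**The case against.** The protocol never names the acid in its proportionality sentence and defers detail to the analysis plan, so naming the analyte may be the detail it left open. That stands as a limit on the claim: there is an inferred commitment to the acid, not an express one. It does not reconcile SAP 9 with 9.1.5.1, and it does not cover the move from a committed to an optional model.

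The parent's position is better than the optional wording suggests. Visual inspection is committed, and Table 3.5 is listed without a condition. That also stands.

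Three stronger readings are tempting.

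- *That acid proportionality would go untested.* Protocol 10.1 sets no formal PK hypotheses, so nothing was to be tested. Table 3.4 summarises acid parameters by dose, Figures 3.4 and 3.7 plot acid concentrations, and Listings 66 and 69 give individual data. A gross departure would be visible; only the slope and its interval are missing.
- *That saturable conversion would bend the acid while the parent looked proportional.* This depends on the share of parent clearance that forms the acid, which the documents do not give. Let that share halve from f0 to f1 between 1 and 40 mg. The parent's ratio to proportional exposure is 1/(1 − f0 + f1), the acid's is f1/f0 times that, and each slope is 1 + ln(ratio)/ln(40). With f0 = 10% the slopes are 1.01 (parent) and 0.83 (acid). With f0 = 90% they are 1.16 and 0.97. Above about 59% the parent departs more than the acid, so no single magnitude is defensible.
- *That the optional wording followed from the data.* The SAP was approved in June 2020, after dosing had ended, and the unblinded members of the dose escalation committee included the sponsor's statistician and pharmacokineticist. Nothing shows that results drove the wording.

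The reach is also limited. The power model uses plasma parameters. Intracellular acid was only ever to be described (Protocol 10.4.3), and the protocol's exposure limits for dose escalation refer to the parent.

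**Conclusion.** The point holds as a specification gap with an undeclared change. SAP 9 and 9.1.5.1 conflict on the analyte, the protocol's committed power model has become optional, and SAP 2.1 records neither. The consequence is that no plasma-acid slope or 90% CI is specified for an active metabolite that is a secondary objective.

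The size is modest: one missing estimate in a descriptive, estimation-only PK analysis. Whether that estimate would be precise is conditional. With the acid quantifiable at all doses and the assumed CVs, the half-width is about 0.05 to 0.10; with quantification only from 10 mg it could reach about 0.29. The first would describe proportionality well. The second might not separate moderate departures from a slope of 1.

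This does not extend to Part C, where only 10 mg was given and proportionality cannot be estimated. The reference to Parts A and C in the title of the model box is a leftover. It does not extend to intracellular acid either.

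**What to change.** In SAP 9.1.5.1, commit to the Part A power model for plasma AUC and Cmax of GSK3358699 and, where quantifiable, GSK3206944. If a data condition is kept, state what it means, for example the minimum number of dose levels and profiles with a quantifiable parameter. State whether Period 4 profiles enter the model. Page Table 3.5 by compound. Add dose-normalised AUC and Cmax plots by compound to the figure list, which has none. Correct the box title to Part A only.

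If the sponsor prefers to keep the parent-only scope or the optional wording, amend SAP 9 to match and record the change with its reason in SAP 2.1.

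The cost is one more run of a model that is already specified, one page-by variable and one added figure, all on data already collected.
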